4. STUDY OBJECTIVES

4.1 Primary Objective

- To evaluate the insulin lispro PK following subcutaneous (SC) doses of LY900014 compared to Humalog (at doses of 7, 15, and 30 U) in healthy subjects.

4.2 Secondary Objectives

- To evaluate the dose proportionality of the 3 dose levels of LY900014 as assessed by insulin lispro PK and GD measures.
- To evaluate the GD during euglycaemic clamp procedure following SC doses of 7, 15, and 30 U of LY900014 compared to Humalog in healthy subjects.
- To evaluate the tolerability of LY900014 in healthy subjects.

4.3 Exploratory Objectives

- Explore the formation of antibodies to insulin lispro.

- To assess C-peptide levels following administration of LY900014 and Humalog.

5. STUDY DESIGN

This is a Phase 1, randomised, subject- and investigator-blind, 6-period complete crossover study in up to 42 healthy subjects to evaluate the PK and GD characteristics across a range of LY900014 doses.

Approximately 34 subjects are expected to complete the study. Each subject will be randomised to 1 of 6 treatment sequences comprising single SC doses of 7, 15, and 30 U of LY900014 or Humalog administered SC in the abdominal wall (Table 1). A minimum of 3 days between study dosing of each consecutive study period will be required for an individual subject. Figure 1 illustrates the study design.

Study governance considerations are described in detail in Appendix 3 of the protocol.

Figure 1. Illustration of Study Design

[figure not shown]

Table 1. Treatment Sequence Example

Treatment Sequence	Period 1	Period 2	Period 3	Period 4	Period 5	Period 6
1	LY 7 U	LY 15 U	H 30 U	LY 30 U	H 15 U	H 7 U
2	LY 15 U	LY 30 U	LY 7 U	H 7 U	H 30 U	H 15 U
3	LY 30 U	H 7 U	LY 15 U	H 15 U	LY 7 U	H 30 U
4	H 7 U	H 15 U	LY 30 U	H 30 U	LY 15 U	LY 7 U
5	H 15 U	H 30 U	H 7 U	LY 7 U	LY 30 U	LY 15 U
6	H 30 U	LY 7 U	H 15 U	LY 15 U	H 7 U	LY 30 U

Abbreviations: H = Humalog; LY = LY900014.

Note: this is only an example table for illustrative purpose; subjects will be assigned a treatment sequence according to the actual treatment randomisation schedule provided to the unblinded site pharmacist.

Subjects will be admitted to the clinical research unit (CRU) on the evening before each dosing day and will remain in the CRU for the duration of the clamp period and until discharge by the investigator. Subjects are expected to fast for at least 8 hours before each dose. Following dose administration, each subject will undergo an euglycaemic clamp procedure of up to 10 hours. Upon completion of the clamp procedures, the subjects will be provided a meal and discharged from the CRU in the evening after medical assessments. Subjects may remain in the CRU if deemed necessary for safety monitoring, as determined by the investigator.

Subjects will be required to attend the CRU on at least 8 occasions:

- screening visit (up to 28 days prior to dosing)
- six treatment visits for the dosing and clamp procedure (study Periods 1 to 6) with a minimum period of at least 3 days between consecutive clamp visits
- follow-up visit (at least 14 days after the last dose), or early discontinuation

In the study, safety assessments and an evaluation of local tolerability at injection sites will be performed as specified in the Schedule of Activities (Section 2 of the protocol). Local tolerability assessments will include injection-site reactions within the following categories: pain on palpation, itching, erythema, oedema, and induration/infiltration.

6. TREATMENTS

The following is a list of the study treatment abbreviations that will be used in the TFLs.

Study Treatment Name	Treatment order in TFL
7 U LY900014 SC	1
15 U LY900014 SC	2
30 U LY900014 SC	3
7 U Humalog SC	4
15 U Humalog SC	5
30 U Humalog SC	6

7. SAMPLE SIZE JUSTIFICATION

7.1 Sample Size Determination for Faster PK Absorption

Up to 42 subjects may be enrolled to ensure that at least 34 subjects complete the study.

Thirty-four completing subjects will provide approximately 96% power to demonstrate a 40% increase in the insulin lispro area under the concentration versus time curve (AUC) from time zero to 30 minutes (AUC[0-30min]) between LY900014 and Humalog. Testing will be done at an alpha level of 0.05 with a 2-sided confidence interval (CI). The variability was estimated using prior internal studies that showed an average log-scale standard deviation (SD) of within-subject difference in AUC(0-30min) of CCI. Analysis of internal data showed a log-scale SD of within-subject difference in time to early half-maximal plasma concentration (early 50% time of maximum observed drug concentration [t_{max}]) of CCI. This sample size provides approximately 98% power to show a 30% reduction in early 50% t_{max} , testing with an alpha level of 0.05 and a 2-sided CI.

In addition, the study is adequately powered to evaluate the GD parameters. There is approximately 80% power to detect a 20% decrease in both time to onset of insulin action (T_{onset}) and time to half-maximal glucose infusion rate (GIR) before time to R_{max} (tR_{max}) (early 50% tR_{max}) and at least 85% power to detect at least a 40% increase in total amount of glucose infused (G_{tot}) over 30 minutes ($G_{tot}[0-30min]$) and G_{tot} over 1 hour ($G_{tot}[0-1h]$).

7.2 Sample Size Determination for Dose Proportionality

Thirty-four completing subjects will provide greater than 95% power to demonstrate dose proportionality of AUC from time zero to 10 hours (AUC[0-10h]) and AUC from time zero to infinity (AUC[0-∞]). This is based on the assumption of a log-normal distribution and an estimate of intrasubject log-scale SD of CCI. There is also approximately 90% power to demonstrate dose proportionality of maximum observed drug concentration (C_{max}), assuming an intrasubject log-scale SD of CCI.

8. DEFINITION OF ANALYSIS POPULATIONS

The “Safety” population will consist of all enrolled subjects who receive at least 1 dose of study drug.

The primary statistical analyses for PK will be conducted on those subjects who receive at least 1 dose of study drug and have measurable insulin lispro concentrations.

The primary statistical analysis for GD will be conducted on those subjects who complete at least 1 clamp procedure.

Supportive analyses will be done on the key parameters for the subjects who complete all treatment periods with evaluable data.

All protocol deviations that occur during the study will be considered for their severity/impact and will be taken into consideration when subjects are assigned to analysis populations.

9. STATISTICAL METHODOLOGY

9.1 General

Data listings will be provided for all data that is databased. Summary statistics and statistical analysis will only be presented for data where detailed in this SAP. For continuous data, summary statistics will include the arithmetic mean, arithmetic SD, median, min, max and N; for log-normal data (e.g. the PK parameters: AUCs and C_{max}) the geometric mean and geometric coefficient of variation (CV%) will also be presented. For categorical data, frequency count and percentages will be presented. Data listings will be provided for all subjects up to the point of withdrawal, with any subjects excluded from the relevant population highlighted. Summary statistics and statistical analyses will generally only be performed for subjects included in the relevant analysis population. For the calculation of summary statistics and statistical analysis, unrounded data will be used.

Data analysis will be performed using [REDACTED].

9.2 Demographics and Subject Disposition

Subject disposition will be listed. The demographic variables age, sex, race, ethnicity, country of enrolment, site ID, body weight, height and body mass will be summarized and listed.

9.3 Pharmacokinetic Assessment

9.3.1 Pharmacokinetic Parameter Estimation

Insulin lispro PK parameter estimates for LY900014 will be calculated using standard noncompartmental methods of analysis. Free serum insulin lispro concentrations will be used to calculate several PK parameters, including C_{max} , t_{max} , time to early half-maximal plasma concentration (early 50% t_{max}), time to late half-maximal drug concentration (late 50% t_{max}), AUC from time zero to 15 minutes [AUC(0-15min)], AUC from time zero to 30 minutes AUC(0-30min), AUC from time zero to 1 hour [AUC(0-1h)], AUC from time zero to 10 hours AUC(0-10h), AUC from time 3 to 10 hours AUC(3-10h) and AUC(0- ∞) will be determined. Additional partial AUCs may be computed as necessary, such as AUC from time zero to 2 hours.

The insulin lispro PK parameters for assessing faster insulin lispro absorption are the early 50% t_{max} and AUC(0-30min).

The insulin lispro PK parameters for assessing reduction in the late insulin lispro exposure are the late 50% t_{max} and AUC(3-10h).

The insulin lispro PK parameters for assessing dose proportionality are the C_{max} , AUC(0-10h), and AUC(0- ∞).

Although attempts will be made to adhere to the scheduled collection times (Section 2 of the protocol), it is recognised that situations arise that may compromise the scheduled times. Parameters will be individually calculated for each subject based on actual collection times and presented using summary statistics.

9.3.2 Pharmacokinetic Statistical Inference

Log-transformed AUCs and C_{max} for insulin lispro will be evaluated to estimate least-squares (LS) geometric means, ratios of LS geometric means between LY900014 and Humalog for each dose level, and their corresponding 95% CIs using the mixed-effects model that includes treatment, dose level, dose level-by-treatment interaction, and period as fixed effects and subject as a random effect.

Example **CC1** code:

```
proc mixed data=pk;
class subject period treatment dose ;
model logpk = treatment period dose dose*treatment / ddfm=kr;
random subject;
lsmeans dose*treatment;
run;
```

The same model without log transformation will be used for the analysis of the PK time parameters (early 50% t_{max} , late 50% t_{max} , and t_{max}). LSmeans, treatment differences in LSmeans, and the corresponding 95% CIs for the treatment differences for each dose will be estimated from the model. The treatment ratios and 95% CIs for the ratios will be calculated using Fieller's theorem.

The analyses described above will also be performed on the population of subjects who completed and had evaluable PK data for all study periods.

In addition, the degree of dose proportionality for insulin lispro will be assessed by fitting the power model (Smith et al. 2000³) to both AUC (AUC[0-10h] and AUC[0-∞]) and C_{max} versus dose for each dose level of LY900014. The estimated ratio of dose-normalised geometric means of PK parameters between the highest and lowest doses will be used to assess dose proportionality. In addition, the slope and its 95% CI and the geometric LSmeans for each dose level tested will be produced. In the event that the power model is not a good representation of the data over the entire dose range tested, alternative models may be investigated. Log-transformed C_{max} and AUC LSmeans, and 95% CI estimates for each dose will be back-transformed to provide the geometric means and the corresponding 95% CIs. The analyses will also be performed using the subset of the subjects who complete all treatment periods with evaluable data.

Example **CC1** code:

```
proc mixed data=pk1;
class subject;
model log_pk = log_dose / alpha=0.05 cl solution outpred=resids ddfm=kr;
random subject;
estimate 'xx mg' intercept 1 log_dose a / alpha=0.05 cl; /*Log value of xx*/
estimate 'yy mg' intercept 1 log_dose b / alpha=0.05 cl; /*Log value of yy*/
estimate 'zz mg' intercept 1 log_dose c / alpha=0.05 cl; /*Log value of z*/
estimate 'zz mg - xx mg' log_dose d / alpha=0.05 cl; /*Difference in log
values of zz and xx*/
estimate 'zz mg - yy mg' log_dose e / alpha=0.05 cl; /*Difference in log
```

```
values of zz and yy*/  
estimate 'yy mg - xx mg' log_dose f / alpha=0.05 cl; /*Difference in log  
values of yy and xx*/  
ods output solutionf=est;  
ods output estimates=estims;  
run;
```

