9.4.2 Glucodynamic Statistical Inference

The GD statistical model will be the same as the model used for the analysis of the PK parameters. The following variables will be log transformed prior to analysis: R_{max} , G_{tot} , $G_{tot}(0-30min)$, and $G_{tot}(0-1h)$ along with any additional partial G_{tot} . For GD parameters that have at least 1 patient with a value equal to zero, an analysis of original scale data (not log-transformed) will be performed as described below for the GD time parameters.

The same model without log transformation will be used for the analysis of the GD time parameters (T_{onset} , tR_{max} , early 50% tR_{max} , late 50% tR_{max}). LSmeans, treatment differences in LSmeans, and the corresponding 95% CIs for the treatment differences for each dose will be estimated from the model. The treatment ratios and 95% CIs for the ratios will be calculated using Fieller's theorem.

The analyses described above will also be performed on the population of subjects who completed and had evaluable GD data for both study periods.

The degree of dose proportionality for the insulin lispro in LY900014 will be assessed by fitting the power model to G_{tot} and R_{max} versus dose for each dose level of LY900014.

The analyses will also be performed using the subset of the subjects who complete all treatment periods with evaluable data.

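### The example power-model code lets subjects differ in level but not in slope, so the 95% CIs for LY900014 dose proportionality are on average too narrow if individual slopes vary.

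*SAP*

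**What the plan says.** Dose proportionality is the first secondary objective (SAP 4.2): "To evaluate the dose proportionality of the 3 dose levels of LY900014 as assessed by insulin lispro PK and GD measures". SAP 9.3.2 names the quantity on which it is judged: "The estimated ratio of dose-normalised geometric means of PK parameters between the highest and lowest doses will be used to assess dose proportionality". It then adds further output: "In addition, the slope and its 95% CI and the geometric LSmeans for each dose level tested will be produced".

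The prose of 9.3.2 does not say which random effects the power model has. Only the example code does. It fits "model log_pk = log_dose / alpha=0.05 cl solution outpred=resids ddfm=kr", a single fixed slope on log dose, with "random subject" as the sole random statement. The comparison of highest with lowest dose comes from the same fit, through "estimate 'zz mg - xx mg' log_dose d / alpha=0.05 cl".

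For glucodynamics, SAP 9.4.2 plans "fitting the power model to G_{tot} and R_{max} versus dose for each dose level of LY900014" and gives no code of its own. Neither document plans a random slope or a check of whether slopes differ between subjects. SAP 9.3.2 allows other models to be explored if the power model fits poorly over the dose range, but that is optional and does not mention slope differences.

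**The concern.** In this crossover a subject who completes the study receives 7, 15 and 30 U of LY900014, so each completer has an individual slope of log response on log dose. The coded model treats these slopes as identical. Any real differences between them go into the within-subject residual and are averaged there with ordinary noise. The uncertainty of the mean slope, however, contains the whole of the between-subject slope variance. The Kenward-Roger option adjusts for estimating the variance components that are in the model. It cannot supply one that was left out.

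At stake is the stated precision of the slope and of the 30 U/7 U ratio for AUC, Cmax, Gtot and Rmax. The error runs one way: the intervals are on average too narrow.

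**Working it through.** **Inputs from the documents.** Doses 7, 15 and 30 U. Completers n = 34 (SAP 7.1). Two-sided 95% CI and random intercept only (SAP 9.3.2).

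**Inputs assumed.** The residual log-scale SD σ is redacted and is taken as 0.20, with 0.30 as an alternative. The between-subject SD τ of the slope is not given and is varied from 0 to 0.30. Data are complete.

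**The plan's own figures.** SAP 7.2 states power above 95% for AUC and about 90% for Cmax. These cannot be reproduced, because the SD is redacted and no acceptance limits are given. If the criterion were a 90% CI within 0.80 to 1.25 with a true slope of 1 (an assumption), they would correspond to σ of about 0.254 and 0.278. With a 95% CI the values would be 0.233 and 0.253. That only shows that the assumed 0.20 to 0.30 is a reasonable bracket.

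**Step 1: spread of log dose.** ln 7 = 1.9459, ln 15 = 2.7081, ln 30 = 3.4012, mean 2.6851. Sxx = 0.7392² + 0.0230² + 0.7161² = 1.0597.

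**Step 2: variances of the mean slope.**
- True: (σ²/Sxx + τ²)/n.
- Reported by the coded model, on average: (σ²/Sxx + τ²·(n−1)/(2n−1))/n. The residual is pooled over 2n−1 = 67 df, of which n−1 = 33 carry slope differences, and 33/67 = 0.49.

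**Step 3: example, σ = τ = 0.20.** σ²/Sxx = 0.04/1.0597 = 0.0377.
- True SE = √((0.0377 + 0.0400)/34) = 0.0478.
- Reported SE = √((0.0377 + 0.0197)/34) = 0.0411, which is 14% too small.

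**Step 4: range at σ = 0.20.** Coverage of the nominal 95% CI comes from 40,000 simulated trials per row. Repeat runs agree to about 0.3 percentage points.

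| τ | True SE | Reported SE | Ratio | Coverage as coded |
|---|---|---|---|---|
| 0 | 0.0333 | 0.0333 | 1.000 | 95.0% |
| 0.05 | 0.0344 | 0.0339 | 0.984 | 94.7% |
| 0.10 | 0.0375 | 0.0354 | 0.945 | 93.7% |
| 0.20 | 0.0478 | 0.0411 | 0.860 | about 91% |
| 0.30 | 0.0613 | 0.0491 | 0.802 | about 88.6% |

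With σ = 0.30, coverage is about 94.4%, 92.7% and 91% for τ = 0.10, 0.20 and 0.30. A t-interval on the per-subject slopes keeps about 95% in every scenario. At τ = 0 it is about 1.5% wider.

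**Step 5: worst case.** As τ grows relative to σ, the SE ratio tends to √(33/67) = 0.702, so the SE is at most about 30% too small. The effective critical value is 0.702 × 1.996 = 1.401. That gives coverage of 83.9% by the normal approximation and 82.9% by the t distribution on 33 df.

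**Step 6: the 30 U/7 U ratio.** The log of the dose-normalised ratio is (slope − 1)·ln(30/7) = (slope − 1) × 1.4553, so its SE is too small by the same factor. For σ = τ = 0.20 and an estimate of 1:
- As coded: exp(±1.996 × 1.4553 × 0.0411) = 0.887 to 1.127.
- With subject slopes: exp(±2.035 × 1.4553 × 0.0478) = 0.868 to 1.152.

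**Step 7: check with fitted mixed models.** REML fits of 150 simulated trials (σ = 0.20, τ = 0.30, no Kenward-Roger adjustment) gave a mean slope SE of 0.0486 with a random intercept and 0.0605 with a random intercept and slope. The empirical SD was 0.0643.

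**The case against.** **The size is assumed.** No slope variance appears in either document and the residual SD is redacted. This stands. The upper scenarios also imply large differences between people. With τ = 0.30, 95% of subjects' own dose-normalised 30 U/7 U ratios would span exp(±1.96 × 0.30 × 1.4553), or 0.42 to 2.35 times the typical value. With τ = 0.10 the span is 0.75 to 1.33. Nothing in the documents supports the wider spread for AUC or Cmax. Protocol 5.4 chose healthy subjects to limit physiological variability.

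**Glucodynamics.** A reader might infer that differing insulin sensitivity makes a common slope unlikely for Gtot and Rmax. The documents do not show this. A proportional difference in sensitivity is a shift in level on the log scale, which the random intercept absorbs. Slopes differ only if saturation or curvature differs between subjects. That is possible, but it is not documented.

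**Consequences.** A reader might also infer that the plan will falsely exclude or falsely confirm a slope of 1. The SAP contains no test of slope = 1 and no acceptance limits, so there is no decision error to quantify.

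**Example code and the poor-fit clause.** The code is labelled as an example, and other models may be tried if the fit is poor. This mitigates little. The code is the only statement of the power model's random effects, and a mean line can fit well while individual slopes differ.

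**Replacing the model by per-subject slopes.** This would not suit as the main analysis. SAP 8 defines the primary PK population as subjects with at least one dose and measurable concentrations, so some may lack one or more LY900014 doses. The t-interval was shown to hold only for subjects with all three.

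**Conclusion.** The point holds in a conditional form. If slopes differ between subjects, the coded model passes only about half of the slope variance into the reported variance, and the 95% CIs of the slope and of the 30 U/7 U ratio are on average too narrow. If slopes vary little relative to the residual, the loss is immaterial. At equal SDs the SE is 14% too small and coverage is about 91%.

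These figures rest on 34 completers, complete data and assumed values for both SDs. The harm is overstated precision for a secondary objective. The figures are not evidence that the stated power is wrong, because it cannot be checked either way. The point estimate does not change in complete data, and the primary LY900014–Humalog comparison uses a different model. The change is worth making because it is cheap and the error has one direction.

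**What to change.** In the power-model code of SAP 9.3.2, replace the random statement by `random intercept log_dose / subject=subject type=un`, keeping `ddfm=kr`. Use a simpler covariance structure if the unstructured one does not converge. State in 9.4.2 that the same model applies to Gtot and Rmax. Keep all subjects of the primary population in the fit.

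Specify the fallback in advance. If the slope variance is estimated as zero or the fit fails, keep the random-intercept fit. Also report the t-interval of per-subject slopes among subjects with all three LY900014 doses, labelled as a supportive, completer-based result.

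**Cost.** One line of code and a sentence or two of text. If slopes do not vary, the CI is about 1.5% wider (shown for the per-subject-slope interval in complete data). With only three observations per subject, the random-slope model may fail to converge, which is why the fallback is needed.

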9.4 Glucodynamic Assessment

9.4.1 Glucodynamic Parameter Estimation

GD assessments will be determined from the glucose clamp procedure, where the GIR over time will be used as a measure of insulin effect. GD analyses will be conducted on those subjects who complete at least 1 clamp procedure.

A locally weighted scatterplot smoothing (LOESS) function will be applied to all individual GIR versus time profiles in each treatment group and/or period using CCI. The fitted data for each subject will be used to calculate the following GD parameters: T_{onset} , maximum GIR (R_{max}), time to R_{max} (tR_{max}), time to half-maximal GIR before tR_{max} (early 50% tR_{max}), time to half-maximal GIR after tR_{max} (late 50% tR_{max}), total amount of glucose infused (G_{tot}), G_{tot} over 30 minutes ($G_{tot}[0-30min]$), and G_{tot} over 1 hour ($G_{tot}[0-1h]$). Additional partial glucose AUCs, such as G_{tot} over 2 hours ($G_{tot}[0-2h]$), G_{tot} from 3 hours to 10 hours ($G_{tot}[3-10h]$), from 4 hours to 10 hours ($G_{tot}[4-10h]$) may be computed as necessary. The values of these GD parameters will be summarised by treatment and/or period through descriptive statistics. Mean LOESS fits of GIR versus time profiles will be generated. The primary GD parameters for earlier PD onset are early 50% tR_{max} , $G_{tot}(0-30min)$, $G_{tot}(0-1h)$, and T_{onset} .

9.4.2 Glucodynamic Statistical Inference

The GD statistical model will be the same as the model used for the analysis of the PK parameters. The following variables will be log transformed prior to analysis: R_{max} , G_{tot} , $G_{tot}(0-30min)$, and $G_{tot}(0-1h)$ along with any additional partial G_{tot} . For GD parameters that have at least 1 patient with a value equal to zero, an analysis of original scale data (not log-transformed) will be performed as described below for the GD time parameters.

The same model without log transformation will be used for the analysis of the GD time parameters (T_{onset} , tR_{max} , early 50% tR_{max} , late 50% tR_{max}). LSmeans, treatment differences in LSmeans, and the corresponding 95% CIs for the treatment differences for each dose will be estimated from the model. The treatment ratios and 95% CIs for the ratios will be calculated using Fieller's theorem.

The analyses described above will also be performed on the population of subjects who completed and had evaluable GD data for both study periods.

The degree of dose proportionality for the insulin lispro in LY900014 will be assessed by fitting the power model to G_{tot} and R_{max} versus dose for each dose level of LY900014.

The analyses will also be performed using the subset of the subjects who complete all treatment periods with evaluable data.

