9.6. Glucodynamics (Euglycaemic Glucose Clamp)

The aim of the euglycaemic glucose clamp is to maintain target glucose levels through infusion of a 20% d-glucose (dextrose) solution after the administration of a dose of insulin. During the glucose clamp, the glucose infusion rate (GIR) will be adjusted to maintain a predetermined target blood glucose concentration for the individual subject. Thus, blood glucose concentrations are kept constant while the GIR varies. The varying GIR will then reflect the GD activity of insulin.

At least 30 minutes before the planned administration of study drug, subjects will be connected to the clamp device **CCI** for continuous blood glucose monitoring to determine their baseline blood glucose. Baseline is defined as the mean of blood glucose concentrations at approximately -6, -4, and -2 minutes (before study drug administration) as measured using **CCI**. After study drug administration, onset of action occurs when blood glucose drops 5 mg/dL (0.3 mmol/L) from baseline (as measured by **CCI**). This blood glucose level 5 mg/dL below baseline will be used as the euglycaemic glucose clamp target level throughout the remainder of the clamp procedure. Subjects will not be clamped to a blood glucose target lower than 63 mg/dL. Therefore, subjects with a mean predose baseline fasting blood glucose below 68 mg/dL (equivalent to a fasting plasma glucose of 76 mg/dL [4.21 mmol/L]) will not be dosed to undergo the clamp procedure but may be rescheduled to a later period. In addition, any study procedures conducted up to that time may be repeated in that later period.

After the onset of action has been reached, a variable IV glucose infusion will be initiated in order to keep blood glucose constant at the target level. The GIR necessary to keep the blood glucose concentration at the target level will be recorded every minute throughout the glucose

clamp. Frequently or at least every 30 minutes throughout the glucose clamp, blood glucose measurements for verification of CCI measurements will be performed using CCI.

The clamp procedure will continue for up to 10 hours after dose or until after blood glucose concentrations return to baseline without any glucose being administered for at least 30 minutes, whichever is earlier. At the end of the clamp procedure, the subject will be given a meal.

All subjects will be medically assessed before discharge from the CRU (see Schedule of Activities [Section 2]).

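### The GD model in SAP 9.4.2 has no term for the period-specific baseline glucose that sets the onset threshold and clamp target, so removable noise may remain in the early GD comparisons

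*SAP*

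**What the plan says.** **How baseline enters the measurements.** Protocol 9.6: "Baseline is defined as the mean of blood glucose concentrations at approximately -6, -4, and -2 minutes" before dosing. Onset of action is a 5 mg/dL fall from that mean, and glucose infusion starts only after onset. The same level then governs the rest of the clamp: "This blood glucose level 5 mg/dL below baseline will be used as the euglycaemic glucose clamp target level". The Schedule of Activities (Protocol section 2) places baseline establishment in the clamp procedure of Periods 1 to 6, so threshold and target are reset in every period.

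**How GD is analysed.** SAP 9.4.2: "The GD statistical model will be the same as the model used for the analysis of the PK parameters". SAP 9.3.2 gives that model as code: "model logpk = treatment period dose dose*treatment / ddfm=kr", with a random subject effect. Time parameters use the same terms untransformed. Protocol 10.3.3.2 agrees. Neither document plans a baseline-glucose covariate, a summary of baseline glucose, or a sensitivity analysis on it. The one GD sensitivity analysis that refers to a baseline (SAP 9.5.10) concerns C-peptide.

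**Stated precision.** SAP 7.1: "There is approximately 80% power to detect a 20% decrease in both time to onset of insulin action" and early 50% tRmax, and "at least 85% power to detect at least a 40% increase in total amount of glucose infused" over 30 minutes and over 1 hour. No SD is shown for any GD parameter.

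**The concern.** PK parameters have no threshold set by the glucose level, so the PK model needs no baseline term. The early GD parameters do have one. If the three-reading mean is high by chance, the 5 mg/dL fall is reached sooner, infusion starts sooner and the target is higher. That shortens T_onset and raises early Gtot. If the mean is low by chance, the reverse happens. The random subject effect removes only the subject's average level, so period-to-period variation remains as residual noise in the LY900014 versus Humalog comparison at each dose.

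T_onset, early 50% tRmax, Gtot(0-30min) and Gtot(0-1h) are the endpoints of the second secondary objective. The two time endpoints have the lowest stated power for the LY900014 versus Humalog comparison. The covariate that could reduce the noise is measured before each period's dose and is already recorded.

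**Working it through.** **1. The plan's own figure.** Without a GD SD, the 80% cannot be reproduced forward, so I solved backward. Inputs are n = 34 completers and two-sided alpha 0.05 (SAP 7.1 states this alpha for PK; I assume it for GD), with a paired noncentral t on 33 df.

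- 80% power needs a standardised difference of 0.495.
- 20% decrease on the log scale: |ln 0.8| = 0.2231. SD of difference = 0.2231 / 0.495 = 0.451. Within-subject SD = 0.451 / √2 = 0.319.
- 40% increase in Gtot at 85% power: ln 1.4 = 0.336, which gives an SD of difference of at most about 0.635.

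**2. Gain for a given correlation.** If r is the within-subject correlation of baseline deviation with outcome, the residual SD is multiplied by √(1 − r²). The documents give no r.

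| r | CI width × | power, 20% decrease (80% unadjusted) | power, 40% Gtot increase (85% unadjusted) |
|---|---|---|---|
| 0 | 1.00 | 80% | 85% |
| 0.2 | 0.98 | 82% | 86% |
| 0.3 | 0.95 | 84% | 88% |
| 0.5 | 0.87 | 90% | 93% |

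I simulated 2,000 trials per setting (34 subjects, six periods, the example sequences of SAP Table 1, true log effect −0.223). Mean estimates were −0.220 to −0.225 with and without the covariate, so there is no bias either way. SE without and with the covariate was 0.0794 and 0.0797 at r = 0, 0.0795 and 0.0761 at r = 0.3 (power 79% and 83%), and 0.0796 and 0.0692 at r = 0.5 (79% and 89%).

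**3. What r could be for T_onset.** Every input here is an assumption: mean T_onset 25 min, so the within-subject SD is 0.319 × 25 ≈ 8 min; error SD of the baseline mean e = 1-2 mg/dL; rate of glucose fall v = 0.5-1 mg/dL per minute. Baseline error then adds an SD of e/v minutes, which is a share (e/v)² / 8² of the within-subject variance.

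The covariate is the observed deviation: reading error plus true day-to-day change (SD D). Threshold and target follow a true change, so only the error part acts through this mechanism. The covariate therefore recovers the fraction e² / (e² + D²) of that share. I take D = 2-4 mg/dL, also assumed.

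| e, v | error share of variance | power if D = 0 | variance removed, D = 2 / D = 4 | power, D = 2 / D = 4 |
|---|---|---|---|---|
| 1, 1 | 1/64 = 1.6% | 81% | 0.3% / 0.1% | 80% / 80% |
| 1, 0.5 | 4/64 = 6.25% | 82% | 1.25% / 0.4% | 80% / 80% |
| 2, 1 | 4/64 = 6.25% | 82% | 3.1% / 1.25% | 81% / 80% |
| 2, 0.5 | 16/64 = 25% | 90% | 12.5% / 5% | 85% / 82% |

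**4. Scale check.** The SAP analyses time parameters untransformed. The implied SD of difference is then 0.2 / 0.495 = 0.404 of the Humalog mean, or 0.404 / √2 × 25 ≈ 7.1 min within subject. The largest entries rise by one to two points (85% to 86%, 90% to 92%) and the others hardly move.

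**5. Size of the reading error.** With a single-reading SD of 1-4 mg/dL (assumed) and independent readings, the SE of a three-reading mean is SD/√3 = 0.58-2.31 mg/dL, or 12-46% of the 5 mg/dL threshold.

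**The case against.** The strongest reply is that no error in the plan has been shown.

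- Randomised sequences keep the contrasts unbiased without the covariate, and the simulation agrees. This stands. A reader might infer that a drifting threshold biases T_onset, and the documents do not support that.
- If the undisclosed GD SDs came from earlier clamps analysed without a baseline term, the stated 80% and 85% already contain this noise. This stands. A reader might infer that the study is underpowered for GD, but the documents do not say where those SDs came from, so no shortfall can be claimed.
- A reader might also suppose that the baseline error is about as large as the 5 mg/dL threshold. No reading SD is given, and the assumed values put it at 12-46%.
- The design already adjusts in part, because threshold and target are relative to baseline. This is right for true day-to-day change, and it is why the covariate is a diluted proxy and the gain falls. It does not cover reading error, which enters the threshold one for one.
- The minutes calculation covers T_onset only, with one rate of fall for doses from 7 to 30 U. This stands: for the other three endpoints only the table by r applies. No mechanism is offered for late or total GD parameters.
- Centring on the subject's mean gives zero for a subject with one clamp, and baselines in Periods 2 to 6 follow earlier doses. The first is harmless. The second matters only with carry-over past the washout of at least 3 days, which the documents do not suggest.

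**Conclusion.** The point holds as a low-cost precision improvement on secondary endpoints. Baseline glucose sets the onset threshold, infusion start and clamp target afresh in each period, and the GD model has no term for it. The possible cost is wider intervals for the four early GD parameters. The primary PK endpoints are unaffected.

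The size is unknown. For T_onset, relative to the stated 80%, power would be about 80-85% with a true day-to-day baseline SD of 2-4 mg/dL. It would be about 90% only if all baseline variation were reading error and the other inputs took their most favourable values. With no correlation it would not change. These figures rest on the assumed mean T_onset, error SD, rate of fall and day-to-day SD, and on true baseline level having no effect of its own on GD response.

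A related point needs reconciling: Protocol 9.6 defines onset by the fall in blood glucose, whereas SAP 9.4.1 lists T_onset among parameters calculated from the fitted GIR curve. Infusion start depends on baseline under both.

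**What to change.** In SAP 9.4.2, for T_onset, early 50% tRmax, Gtot(0-30min) and Gtot(0-1h) only:

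- Add one continuous fixed effect: the period's baseline blood glucose minus the subject's own mean baseline over dosed periods. Use it on whichever scale (log or original) the SAP applies to that parameter.
- Report LSmeans, differences and ratios at deviation zero.
- Keep the model without the covariate as a supportive analysis.
- Summarise baseline glucose by treatment and period.

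This should be prespecified. SAP section 14 shows the sponsor's and the contractor's statisticians as unblinded from randomisation, so a covariate chosen later would be open to challenge.

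The cost is one residual degree of freedom (at r = 0 the simulated SE rose from 0.0794 to 0.0797) and a few extra tables. No additional subjects, samples or procedures are needed.
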